- Previous diagnosis of stage 0-II breast cancer
- Receive some/all care at Dana-Farber Cancer Institute and affiliated satellite sites (Boston's main campus, South Shore Hospital, or St. Elizabeth's Medical Center)
- Completed any active breast cancer therapy ≥ 12 months prior to enrollment (i.e. any chemotherapy, trastuzumab, radiation). Ongoing hormonal therapy or enrollment in survivorship clinical trials (aspirin, exercise, etc) is allowed.
- Age ≥ 75
- Had breast-conserving surgery to treat this cancer
- Provider does not opt out of the patient's enrollment via email notification
- English speaking and reading

For all study aims, we will exclude patients who:

- are unable to consent
- who do not read and write English (for this initial pilot)

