4.0 Study-Wide Number of Subjects*

4.1 For Aim 1.1, we will recruit up to 30 patients and up to 48 providers for the qualitative focus group/interview component, and 5-10 patients for the cognitive interviewing of the tool. For Aim 1.2, we will recruit 45 patients and the providers taking care of those patients.

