will ask the patient to complete the paper ‘post’ surveys in person, by mail, or by email within 7 days of the appointment, concluding the study for that patient. To understand how providers feel about the communication tool, the experience using it, and the comfort with it as a guide for discussions, the clinician will be asked to complete one brief survey per patient enrolled (no provider consent planned but a short introduction to the survey will be provided-see Appendix D), after all of their participating patients have completed their visits. Each patient will be registered to document their participation by DFCI study staff and will receive a \$40 gift card for their participation and clinicians will receive a \$40 gift card after the all surveys for participating patients have been completed. All data will be entered by the CRC into the secure, REDCap.

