Patients: intentions vs. actual decisions for mammography	‘Post’: Examine whether patient intentions for mammography agree with whether mammography is scheduled or not (using chart abstraction)
Patients & Clinicians: Agreement in intentions	‘Post’ for patients and providers: degree of agreement on scores 1-15
Patients & Clinicians: life expectancy wishes	‘post’ for patients and providers: tabulate responses for willingness to discuss

8.5 Primary Outcomes for Aim 1.2: We will focus on the primary outcomes of intentions for mammography and acceptability/ feasibility. We use the sign rank and exact McNemar’s testing to compare the ‘pre’ vs. ‘post’ results for the score for intention and proportion who indicate ‘yes’, respectively. To account for clustering by clinician, we will utilize random effects models if parametric assumptions hold, or alternatively using bootstrap resampling techniques to compute 95% confidence intervals for the change in intention. We anticipate a low number of missed surveys because of the CRC follow-up planned by phone if necessary. If a patient is missed for her ‘pre’ test survey, we will replace her to ensure enrollment of 45 with ‘pre’ and ‘post’ surveys. We will compare characteristics of those with missing surveys and missing questions to those with complete surveys to assess for any notable differences. For feasibility, we will declare the tool feasible if $\geq 75\%$ of patients and physicians report usefulness of the tool.

At the conclusion of this arm, we will have preliminary data on how the communication tool impacted care, its feasibility, and about multiple exploratory, secondary endpoints. If we have difficulties with recruitment of patients or clinicians for this project, we will contact additional clinicians and patients to reach our desired accrual goals. Given the high volume of breast cancer patients and clinicians in our system, we anticipate that accrual will occur with ease.

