24.0 Provisions to Protect the Privacy Interests of Subjects

Study staff will obtain permission from the primary medical oncologist before contacting potential subjects. Only study staff who have completed institutional training and are familiar with the protocol will contact patients for an informed verbal consent. Only staff who have completed training can access Epic or other patient medical record databases. Study staff may conduct a limited review of a patient's medical record in order to confirm eligibility; they may continue to access their records.

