****START RECORDING****

We are working on strategies to better tailor follow up care for women aged 75 and older who have a history of breast cancer. We are a deeply interested in understanding patients' perspectives about how doctors and patients can work together to make decisions about follow up care. In the mail, you should have received a packet. Please keep this packet with you during our conversation. We will have you open the seal on it during our interview, a bit later on.

PART B

BACKGROUND QUESTIONNAIRE (10 minutes)

We will first ask you a series of questions that help us learn about you and your cancer history.

1. Orientation-Memory-Concentration Test Short Blessed Test (SDT) – Scores filled in by interviewer (<http://geriatrictoolkit.missouri.edu/cog/bomc.pdf>)- Entire Part B is for patient one-on-one interviews only

Question	Maximum Error	Score X	Weight
What year is it now?	1	x 4	=
What month is it now? Repeat this phrase and I will ask you to remember it and tell it to me later: John Brown, 42 Market Street, Chicago	1	___ x 3	= ___
About what time is it? (within one hour)	1	___ x 3	= ___
Count backwards 20 to 1	2	x 2	=
Say the months in reverse order	2	x 2	=
Repeat the phrase just given	5	___ x 2	= ___
Total error score = _____			

(If patient scores ≥ 10 , she is ineligible. Thank her for her time, let her know she is not eligible)

We will next ask you about your breast cancer and current follow up plan.

2. When was your breast cancer diagnosed?
- Less than one year ago
 - More than one but less than 2 years ago
 - Between 2 and 5 years ago
 - More than 5 years ago
 - Not sure

PROTOCOL TITLE:

3. Do you still see a medical oncologist or a nurse practitioner/physician assistant in the medical oncologist's office regularly?
 - Yes → If yes, how often?
 - No → If no, when was the last time you had follow up with your medical oncologist?
 - Not sure
4. Do you still see a surgical oncologist or an NP/PA in their office?
 - Yes → If yes, how often?
 - No → If no, when was the last time you had follow up in your surgeon's office?
5. Do you see anyone else for follow up of your cancer?
 - Yes → who?
 - No
 - Not sure
6. Does your primary care provider discuss your breast cancer history with you regularly?
 - Yes
 - No
 - Not sure
 - Other _____
7. Do you still get mammograms?
 - Yes → If yes, when was your last mammogram? → Who typically orders your mammograms? (Oncologist, PCP, someone else?)
 - No → If no, when was your last mammogram?

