****Post-visit Patient Questionnaire****

Study ID: _____

Date: _____

Thank you for agreeing to participate in this study. Now that you have had your visit with your provider, there are a few more questions that we would like you to answer.

If your health care provider asked you right now to make a choice about whether or not to get a mammogram, on a scale from 1-15 how certain are you about whether or not you would choose to get a mammogram in the next

PROTOCOL TITLE:

year? (1 means you are sure you would get a mammogram while 15 means you are sure you would not get a mammogram, if you are unsure please give a number between 1 to 15, 8 is the middle).

1	2	3	4	5	6	7	8	9	10	11	12	13	14	15
Will Get a Mammogram					Unsure					Will Not Get Mammogram				

(**If interview is being done over the phone because the in-person visit was missed, then ask patient: From 1-15, how likely are you to get a mammogram, 1 means you are certain I will get a mammogram and 15 means you are certain you will not get a mammogram. If you are not sure, please give a number between 1 and 15 that best describes how likely you are to get a mammogram)**

2. When do you plan to get your next mammogram?

- Never
- In the next year
- More than 1 year from now but less than 2 years from now
- More than 2 years from now
- Other: _____

The next set of questions are about how you feel about whether or not to get a mammogram and are the same questions we asked you before your visit today. Please say whether you Strongly Agree, Agree, Neither, Disagree, or Strongly Disagree with the statements below.

3. I know which options are available to me for getting tested for breast cancer.

- | | | | | |
|--------------------------|--------------------------|--------------------------|--------------------------|--------------------------|
|  |  |  |  |  |
| Strongly Agree | Agree | Not sure | Disagree | Strongly Disagree |

4. I know the benefits of getting a mammogram.

- | | | | | |
|--------------------------|--------------------------|--------------------------|--------------------------|--------------------------|
|  |  |  |  |  |
| Strongly Agree | Agree | Not sure | Disagree | Strongly Disagree |

5. I know the downsides or risks of getting a mammogram.

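### Scheduling status is taken from the chart alone, so mammograms booked outside the study sites can be missed and the intention–scheduling agreement biased in either direction

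*Protocol*

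**What the plan says.** Protocol Section 8.4, Table 2, defines the row on intentions versus actual decisions as a post-visit comparison: "Examine whether patient intentions for mammography agree with whether mammography is scheduled or not (using chart abstraction". The chart variable has two values, and no other source is named.

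The other relevant provisions are these:

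- **Eligibility (Protocol 3.4).** Partial care at the sites is enough: "Receive some/all care at Dana-Farber Cancer Institute and affiliated satellite sites".
- **Sample (Protocol 4.1).** "For Aim 1.2, we will recruit 45 patients and the providers taking care of those patients".
- **Record access (Protocol 24.0).** "Only staff who have completed training can access Epic or other patient medical record databases", and "Study staff may conduct a limited review of a patient's medical record in order to confirm eligibility; they may continue to access their records". No abstraction window and no request for outside records is described.
- **End of participation (Protocol 5.3).** The post survey is completed "within 7 days of the appointment, concluding the study for that patient".
- **Post-visit patient form (Appendix D, item 2).** It asks "When do you plan to get your next mammogram". That is planned timing, not whether or where an appointment exists.
- **Clinician form (Appendix D).** It asks what was recommended and discussed, not what was ordered or booked.
- **SAP.** It mentions neither this outcome nor chart abstraction.

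Items 31 to 36 of the baseline questionnaire are not in the text available, so the statement about the forms covers only the items shown.

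**The concern.** A two-value chart field cannot separate a woman with no mammogram booked from a woman whose booking is held somewhere the abstractor cannot see. With partial-care patients eligible, the second kind may be present. The protocol's own patient interview script for Aim 1.1 allows for orders from outside oncology: "Who typically orders your mammograms? (Oncologist, PCP, someone else".

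Two records show the consequence:

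- A woman scores 2 (intends a mammogram), and her booking is at an outside facility with no trace in the records searched. She reads as not scheduled, a false disagreement.
- A woman scores 13 (intends to stop), but an outside booking still stands. She also reads as not scheduled, a false agreement.

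This is the only row of Table 2 that sets stated intention against something done. Section 8.5 looks to the pilot for preliminary data on how the tool affected care, and Section 2.7 looks to it to inform a later randomized study. If the booking question is not asked during the short participation window, the plan has no later patient contact in which to recover the answer.

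**Working it through.** The documents give no target, power or expected value for this row, so there is no figure to reproduce. What follows is misclassification arithmetic on stated assumptions.

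**Inputs from the documents**

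- N = 45 (Section 4.1).
- Illustrative shares intending a mammogram: 80% and 57%. Section 2.6 gives these as past-year mammography among survivors aged 65 or older, and among those with an estimated life expectancy of 5 years or less. They are not post-tool intentions and serve only as a range.

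**Assumed inputs, not in the documents**

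- f = share of bookings made outside the sites, 10–30%, taken as equal for intenders and non-intenders.
- c = share of outside bookings still visible in the records searched, 0 or 50%.
- Every woman is treated as a yes or a no; unsure scores (6–10) are left out.

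**Formulas**

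Let q be the share intending a mammogram, a the probability of a booking among them, b the probability of a booking among non-intenders, and m = f(1 − c) the share of bookings missed.

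- True agreement = q·a + (1 − q)(1 − b)
- Observed agreement = q·a·(1 − m) + (1 − q)[1 − b(1 − m)]
- Change = −m[q·a − (1 − q)·b]

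The sign depends on whether booked intenders (q·a) outnumber booked non-intenders ((1 − q)·b).

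**Results with no outside booking visible (c = 0)**

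| Scenario | q·a − (1 − q)·b | Change, f = 10% | Change, f = 30% |
|---|---|---|---|
| q = 0.80, a = 1, b = 0 | 0.80 | −8 points | −24 points |
| q = 0.57, a = 1, b = 0 | 0.57 | −6 points | −17 points |
| q = 0.80, a = 0.95, b = 0.05 | 0.76 − 0.01 = 0.75 | −7.5 (95% to 87.5%) | −22.5 (95% to 72.5%) |
| q = 0.80, a = 1, b = 1 | 0.80 − 0.20 = 0.60 | −6 points | −18 points |
| q = 0.30, a = 0.70, b = 0.50 | 0.21 − 0.35 = −0.14 | +1.4 (56% to 57.4%) | +4.2 (56% to 60.2%) |

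In women, the first row is 45 × 0.80 = 36 intenders, of whom 36 × 0.10 = 3.6 to 36 × 0.30 = 10.8 are misread. The second row is 45 × 0.57 = 25.65, of whom 2.6 to 7.7 are misread. In the third row kappa falls from 0.85 to 0.67 at f = 10% and to 0.42 at f = 30%.

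**Visibility.** With c = 50%, m halves and so does every change: the first row becomes −4 to −12 points. With f = 0 there is no change.

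In all five scenarios the number recorded as scheduled is too low. Agreement falls in four and rises in the fifth.

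**The case against.** The strongest reply is that this fills a silence with the worst reading. The protocol never says that an outside booking is to be coded as not scheduled. Section 24.0 contemplates record databases beyond a single system, and clinic notes may mention appointments elsewhere. Section 5.3 also recruits from participating breast oncologists' schedules and has the coordinator confirm that mammography would normally come up at the visit, which favours women whose imaging is managed there. The interview script comes from a different aim and sample, and it asks who orders the test, not where it is done. This is one exploratory secondary outcome in a 45-patient pilot.

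Much of that stands. Some outside bookings may be seen, which is why the working includes half visibility, and the script is only supporting evidence. But none of it closes the gap. Discussing mammography at the visit does not fix where it is booked. The draft provider email in Appendix H does not ask the confirming question and treats silence as permission. Section 24.0 names no outside records to be searched for this outcome.

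A reader might go further and infer that the error makes the tool appear to reduce mammography use. The documents do not support that. The row measures agreement after the visit. It defines no outcome of use, no pre-visit scheduling measure and no comparison group, so it yields no estimate of a reduction. A booking is also not the same as a mammogram. Nor is there a fixed direction for agreement, since the two kinds of error pull against each other.

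How unsure scores should enter the agreement figure is also unstated, but that is a separate gap with no link to outside care.

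**Conclusion.** The point holds as a gap in ascertainment. Table 2 relies on a two-value chart status, partial-care patients are eligible, and no Aim 1.2 form shown would reveal a booking elsewhere. Where such bookings are missed, scheduling is under-counted. Agreement is then pushed down among women who intend a mammogram and up among women who intend to stop, with a net effect set by the mix.

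The size cannot be known from the documents. The loss of 8–24 points is a conditional illustration: it needs a 10–30% outside share, 80% intending, every intender booked, no non-intender booked and nothing visible outside. Relaxing any of these assumptions changes it, and a low-intention mix can reverse the sign. The primary outcomes, intention and acceptability/feasibility, come from surveys and are untouched. This is a cheap improvement to a secondary outcome, not a flaw that threatens the pilot's main conclusions.

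**What to change.** 1. Add one line to the post-visit patient survey: 'Is your next mammogram already booked, and where?'
2. Replace the two-value status in Table 2 with three values. *Scheduled*: a booking in the chart or by the woman's own report. *Not scheduled*: no booking in the chart and the woman reports none. *Outside/unknown*: neither source settles it.
3. Report the number coded outside/unknown. Give agreement with these women excluded and, as a sensitivity analysis, with all of them counted as scheduled and then all as not scheduled. The two bounds matter because exclusion alone could favour women whose outside booking happened to be visible.
4. State which record systems are searched and the abstraction date relative to the visit. The intention item covers the next year, so a mammogram not yet booked on that date is not evidence of a decision to stop. Outside bookings made after the survey would still go unseen.

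The cost is one survey item, one abstraction field, a few sentences in Table 2 and a somewhat smaller denominator for the main agreement figure. No extra visit or patient contact is needed.

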- 9.3 Survey Instruments. The draft 'pre'/'post' patient surveys and a post-visit clinician survey (all three draft surveys) are in Appendix D. Surveys contain closed-ended questions (except for solicited comments at the end) and are adapted from [name] prior, validated surveys conducted before and after the use of a decision aid for screening mammography in older women.⁶⁶ We will ask about demographics, health literacy and numeracy ('pre' patient), mammography intentions ('pre' and 'post' patient), mammography knowledge ('pre' and 'post' patient), anxiety about recurrence ('pre' patient), acceptability of the communication tool ('pre' patient and clinician), comfort level and interest in discussions about life expectancy ('pre' and 'post' patient and clinician), decisional

PROTOCOL TITLE:

conflict ('pre' and 'post' patient), preferences for a paper/online tool ('post' patient and clinician), and time added to appointments ('post' clinician).

10.0 Data and Specimen Banking – there is no specimen banking as part of this protocol

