****Post-visit Clinician Questionnaire****

Thank you for agreeing to participate in this study. We are going to ask you some questions relating to this particular visit with the patient. All of your answers will be kept confidential, will not be linked to your name for future use, and are for informational purposes only as we try to understand how helpful this tool was in your discussions with patients. Please answer openly and honestly and you can skip any question you prefer not to answer

Study ID _____

Date: _____

Intentions for mammography

1. What did you recommend in terms of mammograms for this patient?

- Continue having mammograms
- Get another mammogram but consider stopping after that
- It is the patient's choice
- To not get a mammogram now but reconsider later
- To stop getting mammograms
- Did not discuss mammograms
- Other: _____

2. Before the visit, what did you think you would recommend?

- Continue having mammograms
- Get another mammogram but consider stopping after that
- It is the patient's choice
- To not get a mammogram now but reconsider later
- To stop getting mammograms
- I did not think I would discuss mammograms
- Other: _____

3. During the visit today, did you discuss any of the following (circle each answer):

- | | | | |
|--|-----|----|----------|
| • Pros of mammograms? | Yes | No | Not sure |
| • Cons of mammograms? | Yes | No | Not sure |
| • The patients individual risk of in-breast, pre-cancer or invasive cancer events? | Yes | No | Not sure |
| • Family history? | Yes | No | Not sure |
| • Life expectancy? | Yes | No | Not sure |

PROTOCOL TITLE:

- Any other relevant discussion points you discussed?
-

3A. If yes to discussing life expectancy, how did this go? Check any that apply:

- Helpful to patient
- Helpful to me
- It was uncomfortable
- It was comfortable
- Made decision-making easier for mammogram
- Made decision-making harder for mammogram
- Neutral effect on decision-making
- Other _____

3B. If no to discussing life expectancy above, why not? Check any that apply

- It didn't come up
- I was uncomfortable talking about it
- Patient did not want to discuss it
- Patient was anxious
- Patient healthy so I didn't think it was important
- I didn't have time
- I didn't think it was important for this discussion

Questions about the Communication Sheet (with regard to its use during this visit with the patient)

4. The length of the communication sheet was

- | | | | | | |

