## Statistical Analysis Plan:

*Pre-visit* patient surveys collected demographics, health literacy, numeracy, and preferences for decision-making roles. *Post-visit* surveys included general guide feedback (e.g., length, clarity). Both surveys inquired about intentions for mammography plus past and current (study visit) experiences and comfort level with life expectancy discussions.

From *post-visit* clinician surveys, in addition to acceptability, we described clinician responses for each participating patient for questions that were relevant to a particular patient (e.g., “What did you recommend in terms of mammograms for *this* patient?”, “Did you discuss the pros [and cons] of mammography”). In addition to descriptive analyses and extraction of explanatory comments (when provided), we used t-tests to examine changes in patient decisional conflict around mammography from the pre- and post-survey to inform design of a future trial of the guide. All analyses were conducted using SAS.

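### Patient-clinician agreement in intentions is defined on 1-15 scores, but the clinician form has no 1-15 item; separately, the protocol gives two completion times for that form

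*Protocol*

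**What the plan says.** In Table 2 (Section 8.4), one secondary outcome for Aim 1.2 is patient-clinician agreement in intentions. It is to come from the post-visit forms of both parties and is defined as "degree of agreement on scores 1-15". Section 8.5 places it among "multiple exploratory, secondary endpoints".

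The first item of the post-visit patient form asks "on a scale from 1-15 how certain are you about whether or not you would choose to get a mammogram in the next" year, answered from 1 to 15. The post-visit clinician form has a block headed "Intentions for mammography" with two items: "What did you recommend in terms of mammograms for this patient" and "Before the visit, what did you think you would recommend". Each offers seven response categories.

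Section 9.3, which maps content to forms, gives "mammography intentions ('pre' and 'post' patient" and names no clinician for that topic, though it does for others, such as acceptability of the tool. The SAP states that "we described clinician responses for each participating patient for questions that were relevant to a particular patient" and names no agreement statistic or coding.

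On timing, Section 5.3 has the clinician fill in one form per patient once all of that clinician's enrolled patients have been seen. Appendix H, the draft email to providers, tells clinicians they will be surveyed as each encounter ends. Items 3 and 11 of the form are worded as if the visit took place that day.

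**The concern.** Agreement on a 1-15 scale needs two 1-15 scores per pair. If only the patient supplies one, the outcome has no value for any pair. Whoever analyses it must drop it or replace it with a different comparison. A replacement needs decisions that neither document makes: which recommendation categories match which part of the patient scale, and what to do with answers that point in no direction. If those decisions are made after the answers have been seen, a reader cannot tell how far the result depends on them.

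The completion time matters because most clinician items concern one particular visit: what was recommended, what was expected beforehand, which topics came up, and whether the visit ran longer. Two sites following different parts of the protocol could collect these answers at different distances from the visit.

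**Working it through.** The plan gives no figure to reproduce, so the check compares the passages item by item.

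**Is there a clinician 1-15 score?**

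- Patient post-visit form: 1 item on a 1-15 scale (the first).
- Clinician items 1 and 2: seven categories each. Five are recommendations, one of which leaves the decision to the patient. The others are a not-discussed (item 2: not expected to be discussed) option and an open 'Other'.
- Clinician item 3, with 3A and 3B: yes/no/not sure, then check-all lists.
- Clinician items 4 to 9: ordered categories on length, amount, clarity, balance, helpfulness and recommending the tool.
- Clinician items 10 to 12: preferred format, effect on visit length, free text.

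Count of 1-15 items: 0 of 12. The items run consecutively from 1 to 12 with no sign of removed text, so this is not a gap left by PDF extraction. Section 9.3 independently points the same way.

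Pairs computable as defined = pairs with a 1-15 score on both sides = 0 of 45.

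**Can existing items stand in?**

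- Patient item 1 against clinician item 1 compares an intention with a recommendation. The decision-is-the-patient's, not-discussed and 'Other' options have no place on a 1-15 scale.
- Patient item 44 against clinician item 1 is the closest match in wording: five shared recommendation options plus 'Other', with one extra not-discussed option for clinicians. It measures whether the two parties report the same recommendation, which is a different quantity from agreement in intentions.

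**What would a substitute's statistic need?**

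- Chance correction. With two directional categories and the same proportion p leaning towards mammography on both sides, chance agreement is p² + (1 − p)². Section 2.6 reports past-year mammography in nearly 80% of survivors aged 65 or over, and in 57% of those with an estimated life expectancy of 5 years or less. Taking these as p (an assumption, since they describe past use and not intentions), chance agreement is 0.80² + 0.20² = 0.68 and 0.57² + 0.43² = 0.51. This shows only why raw percent agreement is hard to read; it does not predict this study's result.
- Clustering. Section 5.3 plans 10-12 clinicians, so 45 pairs average 45/12 = 3.75 to 45/10 = 4.5 per clinician. Section 8.5 already allows for clinician clustering in the intention analysis; the agreement interval should do the same.

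**Timing, side by side**

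- Section 5.3: all forms deferred until the clinician's last enrolled patient has been seen.
- Appendix H: each form at the close of its encounter.
- Form wording: same day.

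For a clinician with more than one enrolled patient, Section 5.3 and Appendix H cannot both be followed.

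**The case against.** The outcome is exploratory, belongs to a single-group pilot, is not in the stated hypothesis, and has no threshold or decision attached. The forms are labelled drafts, and the SAP treats clinician answers descriptively. On this view Table 2 has one outdated cell. All of that stands as a limit on importance. It does not supply the missing score: neither document adds an item or withdraws the outcome.

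Appendix H is only a draft email, while Section 5.3 is the procedure. That is a fair reason to give Section 5.3 more weight, but the form's own wording sides with the email.

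Deferred completion also has something in its favour. Section 5.3 wants the tool used without specific instructions. A form completed after each visit shows the clinician a checklist of pros, cons and life expectancy, and asks why life expectancy was not raised, before the next enrolled patient. That could alter later visits and those patients' post-visit scores. The protocol does not give this as its reason, but the risk is real, so completion after each visit cannot be treated as free.

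Four stronger readings are tempting and should not be drawn:

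- *The coding choice would move percent agreement by a large, known amount.* The documents give neither the number of non-directional answers nor an agreement rate, so any such figure would rest on invented inputs.
- *Most clinician forms would suffer recall error.* Section 5.3 fixes the order of completion, not the delay. Visits could fall close together, and Section 8.5 allows extra clinicians.
- *A substitute was going to be chosen after the data were seen.* That is a risk left open; nothing in the documents shows that one was planned.
- *The primary result is compromised.* The primary intention analysis uses patient scores only. The clinician form also has a helpfulness item, but the protocol does not tie its 75% usefulness criterion to that item, so the point is not extended there.

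**Conclusion.** The agreement outcome cannot be computed as written: 0 of 12 clinician items give a 1-15 score, and 0 of 45 planned pairs can enter. This rests on the clinician form as printed in Appendix D and on Section 9.3; a later form with an added item would resolve it, but neither document contains one. No effect size can be stated beyond that count. The completion-time conflict between Section 5.3, Appendix H and the form's wording is also real, with consequences of unknown size and direction. The primary patient intention analysis does not use clinician scores. Both points are worth correcting because the corrections are small, not because a main conclusion depends on them.

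**What to change.** Agreement outcome, one of two routes:

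- If the clinician form can still be changed, add one 1-15 item with the patient form's anchors and its one-year horizon. Table 2 then stands, with the agreement statistic named.
- If the forms are already in use (the SAP is written in the past tense), restate the Table 2 outcome as 'patient intention versus clinician recommendation': patient post-visit item 1 in its 1-5, 6-10 and 11-15 bands against clinician item 1. Fix in writing, before the two sides are cross-tabulated, which combinations count as agreement. Show the full cross-table. Give the patient-decides, not-discussed and 'Other' answers separate rows, scored neither as agreement nor as disagreement. Report percent agreement with its denominator, a chance-corrected measure such as kappa, and an interval that allows for clustering by clinician, for example by resampling clinicians. Patient item 44 against clinician item 1 may be added, labelled as agreement on the recommendation.

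Timing: reconcile Section 5.3, Appendix H and the form's wording to one completion time. State the trade-off considered: recall error if completion is deferred, prompting before later enrolled patients if it follows each visit. Use the form's existing date field to report the time from visit to completion.

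Cost: one item on a draft form, or one Table 2 cell and a short coding rule, plus wording edits so that the three timing statements match. Clinicians complete the same number of forms.
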